- 17. Serious adverse reaction or serious hypersensitivity to any drug or the formulation excipients; including intolerance to itraconazole, rabeprazole, rifampicin and omeprazole.
- 18. Presence or history of clinically significant allergy requiring treatment, as judged by the investigator. Hayfever is allowed unless it is active
- 19. Donation or loss of greater than 400 mL of blood within the previous 3 months
- 20. Subjects who are taking, or have taken, any prescribed or over-the-counter drug (other than 4 g per day paracetamol) or herbal remedies in the 14 days before IMP administration (See Section 11.4). Exceptions may apply on a case by case basis, if considered not to interfere with the objectives of the study, as agreed by the principal investigator (PI) and sponsor's medical monitor.
- 21. Failure to satisfy the investigator of fitness to participate for any other reason

Exclusion criteria 6, 9, 10, 14, 16, 18, 20 and 21 from the list above will be re-assessed at admission/pre-dose, as applicable.

Healthy subjects who do not meet the inclusion/exclusion criteria for a study should not be enrolled into the study without exception.

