9.6 Additional Study Restrictions

The following additional restrictions will be in place for the duration of the study:

- Subjects must abstain from alcohol during the 24 h prior to screening and the 24 h
 prior to admission in Period 1, and 24 h prior to commencing NIMP treatment in Part 1
 Periods 2 to 4 and Part 2 Period 2, until discharge for each treatment period
- Subjects must not drink liquids or eat food containing grapefruit or cranberry from 24 h prior to admission in Period 1, and 24 h prior to commencing NIMP treatment in Part 1 Periods 2 to 4 and Part 2 Period 2, until discharge for each treatment period
- 3. Subjects must not drink liquids or eat food containing caffeine or other xanthines from 24 h prior to admission until discharge for each treatment period

- 4. Subjects should refrain from eating food containing poppy seeds for 48 h prior to screening and for 24 h prior to admission until discharge for each treatment period
- 5. Subjects must not take part in any unaccustomed or strenuous exercise from the 72 h before the screening visit and then from 24 h prior to admission until discharge for each treatment period.

10 Study Procedures

Study procedures will be performed as detailed in the study schedule of assessments in Appendix 2 and Appendix 3, and in accordance with Quotient Sciences standard operating procedures unless otherwise stated in this protocol.

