10.2 Admission and Pre-dose Procedures

The identity of the subjects will be confirmed at admission and pre-dose.

In addition, the ongoing eligibility of subjects will be re-assessed at admission/pre-dose, as described in Sections 9.2 and 9.3.

Reserve subjects for the first dose occasion, in any group, will not require admission procedures to be repeated, if dosing is within 2 days.

Part 1: subjects will be admitted to the clinical unit on the morning before IMP administration (Day -1) for Periods 1, 2 and 4, and on the evening before IMP administration (Day -1) for Period 3.

Part 2: subjects will be admitted to the clinical unit on the evening before IMP administration (Day -1) for both periods.

The admission and pre-dose procedures are presented in Appendix 2 and Appendix 3

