Appendix 2 Part 1 Study Flow Chart

	Screening	Outpatient Visit																		
			Admissiona	on ^a Resident in Clinic														Discharge	Follow-	
Study Day	-28 to -2	-3 (Period 3)	-1			2						2	3	up						
		-9 (Period 4)		Pre-dose		Time Relative to KD025 Dosing (h)													- Visit ^b	
		-5 (Period 4)			0	0.5	1	1.5	2	3	4	5	6	8	10	12	24	36	48 -	1
General Assessments																				
Informed Consent	X	•																		
Medical History	X		Х																	
Weight and Height	X		Χc													l				
Vein Assessment	Х																	\square		
Carbon Monoxide Breath Test	X		Х																	
Drug Screen	X		X		L															
Alcohol Breath Test	X		Х					 								L	 			
Non-IMP Administration ^d		Χq	Χq	Χq	Χď												Χq		Χď	
IMP Administration ^e					X															
Safety Assessments				'										,					,	
Physical Examination	X																			X
Safety Labs ^f	X	Χa	X ^h																Χ	X
Urinalysis	X	Xa	Xh																Χ	X
ECG ⁱ	Х		Х	Xi					X		Χi					Х				X
Vital Signs ^j	Х		Х	Х					Х		Х					Х				X
Concomitant Medication	-																			→
Adverse Events	—														_					 
PK Assessments																				
Plasma Samples for KD025 and metabolites KD025m1 and KD025m2				х		х	Х	х	х	х	Х	х	х	х	х	х	Х	х	х	

Footnotes on next page

^a Morning of Periods 1, 2 and 4, evening of Period 3

^b A follow-up visit will take place 3 to 5 days post-final discharge

^c Weight only at admission

d Itraconazole on Day 3 (of Period 1; or Day -7 of Period 2 if washout period is extended) and continuing from Day -6 to -1 (Period 2); rabeprazole from Day -3 to -1 (Period 3); rifampicin from Day -9 to -1 (Period 4). On Day -1, subjects will take itraconazole (Period 2) and rifampicin (Period 4) in the clinic after admission, and rabeprazole (Period 3) at home prior to admission.

e IMP will be administered in the fed state. Co-administration with NIMP in Periods 2 and 3; itraconazole will be administered at the same time as IMP in Period 2 (fed state) and rabeprazole will be administered approximately 2 h prior to IMP in Period 3 (fasted state)

F Haematology and clinical chemistry; virology and creatinine clearance at screening only

g Day -3 (Period 3) and Day -5 (Period 4) only

h Periods 1, 2 and 4 only

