### 10.5.1 Summary Tables for Laboratory Evaluations

Haematology and clinical chemistry data will be summarised (mean, SD, median, minimum, maximum and n) for each laboratory parameter at each time point, including changes from baseline at the 48 h (Day 3) post-baseline time point by treatment. For the purposes of laboratory evaluations baseline is defined as follows:

- for Part 1, Periods 1, 2 and 4: Day -1, Admission for each relevant period
- for Part 1, Period 3: Day -3, Outpatient Visit
- for Part 2, Periods 1 and 2: Day 1, pre-dose for each relevant period

Shift tables from baseline to the 48 h post-baseline time point (with respect to the number and percentage of subjects with values below, within or above the reference range) will be presented by treatment. Percentages will be based on the number of subjects with measurements at baseline and the 48 h post-baseline time point.

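### In Part 1 Period 3 the safety-laboratory baseline (Day -3) is drawn before the exercise restriction begins, unlike every other laboratory baseline in the study

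*Protocol*

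**What the plan says.** **Exercise.** Protocol section 9.6, item 5, sets two windows: "Subjects must not take part in any unaccustomed or strenuous exercise from the 72 h before the screening visit and then from 24 h prior". The second window reads in full: "then from 24 h prior to admission until discharge for each treatment period". In the same list, items 1 and 2 (alcohol; grapefruit and cranberry) use a different starting point for Periods 2 to 4: "24 h prior to commencing NIMP treatment in Part 1".

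**Admission.** Protocol section 10.2 admits Part 1 subjects in the morning of Day -1 for Periods 1, 2 and 4, but "on the evening before IMP administration (Day -1) for Period 3". Section 8.1.1 puts the Period 3 outpatient visit on the morning of Day -3.

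**Bloods.** In the Part 1 flow chart (Protocol Appendix 2), footnote h limits admission safety laboratory tests to Periods 1, 2 and 4. The outpatient tests are governed by "g Day -3 (Period 3) and Day -5 (Period 4) only". CK, AST and ALT are in the chemistry panel (Appendix 1).

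**Analysis.** SAP section 10.5.1 summarises change from baseline and shifts at 48 h by treatment. Its baseline is the Day -1 admission sample for Periods 1, 2 and 4, but "for Part 1, Period 3: Day -3, Outpatient Visit".

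**The concern.** The four Part 1 treatment columns in the laboratory tables are laid out alike, but one baseline is taken under a different condition. For KD025 alone, with itraconazole and with rifampicin, the baseline follows about a day of restricted exercise. For KD025 with rabeprazole, no restriction is in force before the baseline.

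If recent hard exercise raises CK, AST or ALT, a raised Day -3 value would shrink a true rise at 48 h or show a fall that has nothing to do with treatment, and only in the rabeprazole column. Protocol section 6.4.1 names raised ALT and AST as the most common adverse events with KD025, so these are the laboratory changes a reader will look at. The documents do not state the enzyme response to exercise. They do show, through the 72 h rule at screening, that exercise was thought worth restricting before that visit.

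**Working it through.** The plan states no figure on this point, so the check is a timeline. Day numbers come from the documents, and there is no Day 0. The documents give no clock times. I assume 07:00-11:00 for a morning visit, 17:00-21:00 for evening admission and 08:00 for KD025 dosing.

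**1. When the Period 3 restriction starts.** Admission on Day -1 at 17:00-21:00, minus 24 h, gives Day -2 at 17:00-21:00.

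**2. Gap between the baseline sample and that start.**
- Shortest: Day -3 11:00 to Day -2 17:00 = 24 + 6 = 30 h.
- Longest: Day -3 07:00 to Day -2 21:00 = 24 + 14 = 38 h.

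The sample falls outside the window under every assumed combination.

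**3. Whether the Period 2 restriction still covers it.** That restriction ends at Period 2 discharge (Day 3). The minimum washout after Period 2 is 8 days, and how it is counted is open to reading:
- KD025 dose to KD025 dose: Period 3 Day 1 is Period 2 Day 9, and Day -3 is Day 6, so 3 days after discharge.
- Last itraconazole (Day 2) to KD025: Day 1 is Day 10, and Day -3 is Day 7, so 4 days after.
- Last itraconazole to first rabeprazole: Day -3 is Day 10, so 7 days after.

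With the stated minimum washout, the Period 2 restriction does not reach Day -3.

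**4. Restriction in force before each SAP laboratory baseline.**

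| Baseline | Sample | Restriction before it |
|---|---|---|
| Part 1 Periods 1, 2, 4 | Day -1, morning admission | about 24 h |
| Part 1 Period 3 | Day -3, outpatient | 0 h |
| Part 2 Periods 1, 2 | Day 1 pre-dose | about 35-39 h |

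For Part 2, Day -2 at 17:00-21:00 to Day 1 at 08:00 is 39 down to 35 h.

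**5. The post-baseline sample.** From Day -2 at 17:00-21:00 to 48 h after an 08:00 dose (Day 3, 08:00) is 87 down to 83 h, about 3.5 days. The 48 h value is inside the restriction and the baseline is not.

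**6. After the fix.** The first rabeprazole dose is on the morning of Day -3. Starting 24 h earlier puts the restriction at the morning of Day -4, so the Day -3 sample has about 24 h before it, matching the Day -1 baselines.

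**The case against.** The strongest reply is that nothing here is shown to matter. No passage says how far exercise moves CK, AST or ALT, or for how long. Safety is a secondary objective, the summaries are descriptive, and the SAP plans no between-treatment test of laboratory change. Individual values and out-of-range listings are produced with high and low flags, so a raised Day -3 result would be visible. Period 3 is a single dose, KD025 exposure is about 80% lower with rabeprazole (Protocol section 6.1), and liver events generally appeared after 16 to 36 days of dosing (section 5.3.2). All of this stands and keeps the point small. It does not make the baselines alike.

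One might also say that section 9.6 opens by applying its restrictions for the whole study. Item 5 then sets its own start and stop times, so the opening line does not close the gap.

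A reader might infer more than the documents support:

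- **That the Day -3 baseline is uncontrolled altogether.** It is not. Alcohol and grapefruit are restricted from 24 h before NIMP, and scheduled bloods follow an 8 h fast (section 14.5.1). Only exercise is missing.
- **That an exercise artefact could cost a subject's rabeprazole comparison.** Section 9.3 says "Exclusion criteria 6, 9, 10, 14, 16, 18, 20 and 21 from the list above will be re-assessed at admission/pre-dose, as applicable", but does not name the Day -3 visit. Criterion 9 depends on the investigator's judgement, section 14.5.6 allows repeat sampling, and the ALT withdrawal limit in section 8.3 is more than 3 times the upper reference limit. Such a loss is speculative.
- **That 72 h is the standard to apply.** No Part 1 period baseline has a required 72 h. Imposing it on Period 3 alone would replace one asymmetry with another.
- **That the Day -5 (Period 4) and follow-up bloods share the problem.** They feed no change-from-baseline or shift analysis in the SAP.

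**Conclusion.** The point holds as a minor design gap. Part 1 Period 3 is the only laboratory baseline in either part with no exercise restriction before it: 0 h, against about 24 h for the other Part 1 baselines. The sample precedes the restriction by 30-38 h under the assumed clock times. That the sample falls outside the window needs only a morning visit on Day -3 and an evening admission on Day -1, both of which the protocol states.

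The consequence is confined to the Period 3 CK, AST and ALT change-from-baseline and shift summaries. Its size cannot be derived from the documents, and its direction rests on the assumption that exercise raises these enzymes. The primary PK comparison of KD025 with and without rabeprazole is not affected.

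**What to change.** In Protocol section 9.6, item 5, start the Part 1 Period 3 restriction at 24 h before the first NIMP dose and run it to discharge, using the same anchor as items 1 and 2. Update the subject instructions to match.

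For subjects who have already completed Period 3, add a footnote to the Period 3 laboratory tables saying that the Day -3 outpatient baseline was not exercise-restricted. Protocol section 6.1 already reports preliminary rabeprazole results for 21 subjects, out of 40 planned. If Part 1 dosing is complete, the footnote is the only part that still applies. While editing, correct the footnotes to mock Tables 14.4.1.1 and 14.4.1.2, which label the Day -3 baseline as an admission sample.

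The cost is one clause and one footnote, with no change to visits, sample size or models. Volunteers lose a further 24 + 30 = 54 to 24 + 38 = 62 h of strenuous exercise, about 2.3 to 2.6 days. The Period 3 baseline would also differ between subjects treated before and after the change, which the footnote should say.

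The change does not make the baselines alike in every respect. The Period 3 baseline falls on the first rabeprazole day, with its order relative to that dose unstated, while those of Periods 2 and 4 follow several days of NIMP.

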10.1 Screening

Within the 28 days preceding first dose, all subjects will be required to undergo a screening visit. Screening procedures will be carried out in accordance with the study flow chart in Appendix 2 and Appendix 3.

If the start of the study is delayed for any reason so that the interval between screening and first dose exceeds 28 days, all or part of the screening procedures may be repeated at the discretion of the investigator.

Subjects previously screened generically may participate in this study provided they meet the subject selection criteria. Procedures required by this protocol will only be done if they were not performed during generic screening. All screening data must be obtained within 28 days prior to administration of study medication, as stipulated above.

10.1.1 Subject Re-Screening

This study permits the re-screening of a subject who has discontinued the study as a pre-treatment failure (ie subject has not been treated); the reason for failure must be temporary and expected to resolve. If re-screened, the subject must be re-consented.

10.2 Admission and Pre-dose Procedures

The identity of the subjects will be confirmed at admission and pre-dose.

In addition, the ongoing eligibility of subjects will be re-assessed at admission/pre-dose, as described in Sections 9.2 and 9.3.

Reserve subjects for the first dose occasion, in any group, will not require admission procedures to be repeated, if dosing is within 2 days.

Part 1: subjects will be admitted to the clinical unit on the morning before IMP administration (Day -1) for Periods 1, 2 and 4, and on the evening before IMP administration (Day -1) for Period 3.

Part 2: subjects will be admitted to the clinical unit on the evening before IMP administration (Day -1) for both periods.

The admission and pre-dose procedures are presented in Appendix 2 and Appendix 3

10.3 Study Day Procedures

10.3.1 Blood Volume

[figure not shown]
The total blood volume for each subject will not exceed 550 mL in a 4 week period. The first 0.5 mL of blood withdrawn via cannula will be discarded.

10.3.2 Timing of Procedures

There are times where the protocol requires more than one procedure to be completed at the same time point. In these instances the following will apply to post-dose time points:

Pharmacokinetic samples should take priority over other procedures scheduled at the same time point.

As guidance, the preferred order of assessments is:

Electrocardiograms should be taken prior to vital signs when both measurements are scheduled at the same time point. Other assessments, eg physical examinations, will be performed within the required time windows.

All safety assessments will be timed and performed relative to the start of IMP dosing.

10.3.3 Discharge from the Clinical Unit

A subject will be allowed to leave the premises following completion of study-specific procedures at 48 h post-IMP dose (Day 3), providing that:

- no AEs have been reported during the study visit
- the subject responds in the affirmative when asked if they are feeling well

If any of these conditions are not met, then the subject will only be allowed to leave the clinical unit with the authorisation of the investigator or appropriately qualified delegate.

10.3.4 Outpatient Visits

Part 1

Subjects will be asked to attend the clinical unit for outpatient visits on Day-3 of Period 3, and Days -9 and -5 of Period 4 for NIMP administration and home supplies, as well as the assessments described in Appendix 2.

Part 2

If the minimum washout period is extended, subjects will be asked to attend the clinical unit for an outpatient visit on Day -3 of Period 2 for NIMP administration and home supplies, as well as the assessments described in Appendix 3. Otherwise, subjects will receive the first dose of omeprazole at discharge from Period 1.

10.3.5 Medical Supervision

A physician will be responsible for the clinical aspects of the study and will be available at all times during the study. In accordance with the current Association of the British Pharmaceutical Industry guidelines, each subject will receive a card stating the telephone number of the investigator.

10.3.6 Follow-up

A follow-up phone visit will take place 3 to 5 days after final discharge to ensure the ongoing wellbeing of the subjects. If a subject reports any AEs which can present a cause for concern, they will be required to attend the clinic for a further follow-up assessment (as an unscheduled visit). Completion of the last follow-up visit (including any unscheduled) will be considered the end of the study.

11 Dosing of Subjects

11.1 Food and Fluid Intake

Water will be allowed ad libitum on the day of dosing. For Part 1 decaffeinated fluids will be allowed ad libitum from lunch time on the day of IMP dosing. For Part 2, decaffeinated fluids will be allowed ad libitum from lunch time on the day of dosing until 1 h before and then from 1 h after the evening dose.

If, for technical reasons, IMP dosing is delayed for more than 2 h beyond the expected dosing time, subjects may receive 200 mL of Lucozade Sport at the originally scheduled dosing time, or earlier if possible.

11.1.1 Investigational Medicinal Product Dosing

Part 1

Breakfast will be controlled by clinical staff members on IMP dosing days for each treatment period (Day 1). The start and stop time of the breakfast must be recorded and where less than 100% of the breakfast has been consumed, the percentage consumed must be recorded.

Subjects will be provided with a light snack on the evening of admission days for each treatment period (Day -1) and will fast from all food and drink (except water) until the following morning, when they will be provided with a standard breakfast. The breakfast should be consumed over a maximum period of 25 min, with dosing occurring 30 min after the start of breakfast. Subjects should be encouraged to eat their meal evenly over the 25 min period. It is acknowledged that some subjects will take less time to eat, but dosing should still occur 30 min after the start of breakfast.

Lunch will be provided at approximately 4 h post-IMP dose, an evening meal at approximately 9 h post-IMP dose and an evening snack at approximately 14 h post-IMP dose. On subsequent days, meals will be provided at appropriate times.

Part 2

In Part 2 the IMP will be administered BID and given in the fed state.

Breakfast will be controlled by clinical staff members on IMP dosing days for each treatment period (Day 1). The start and stop time of the breakfast must be recorded and

where less than 100% of the breakfast has been consumed, the percentage consumed must be recorded.

Subjects will be provided with a light snack on the evening of admission days for each treatment period (Day -1) and will fast from all food and drink (except water) until the following morning, when they will be provided with a standard breakfast. The breakfast should be consumed over a maximum period of 25 min, with dosing occurring 30 min after the start of breakfast. Subjects should be encouraged to eat their meal evenly over the 25 min period. It is acknowledged that some subjects will take less time to eat, but morning dosing should still occur 30 min after the start of breakfast.

Subjects will be dosed in the evening following the evening meal. Evening dosing will occur 30 min after the start of the evening meal (ie, dosing at 12 h post-morning dose; meal to be started 11 h and 30 min post-morning dose). Decaffeinated fluids will be allowed ad libitum from lunch time on the day of dosing until 1 h before and then from 1 h after the evening dose.

Lunch will be provided at approximately 5 h post-morning IMP dose and an evening snack at approximately 14 h post-morning IMP dose. On subsequent days, meals will be provided at appropriate times.

11.1.2 Non-Investigational Medicinal Product Dosing

Part 1

Subjects will take itraconazole for 9 consecutive days; on Day 3 of Period 1 and from Day -6 to Day 2 of Period 2. All doses of itraconazole should be taken with approximately 240 mL water at approximately the same time each morning following breakfast; when co-administered with IMP on Day 1, a total of 240 mL water should be taken.

Subjects will take rabeprazole for 4 consecutive days; from Day -3 to Day 1 of Period 3. All doses of rabeprazole should be taken with approximately 240 mL water. On Days -3 to -1 (BID dosing days) subjects should take rabeprazole at approximately the same time each morning following breakfast, and following an evening meal. On Day 1, rabeprazole will be administered in the fasted state, approximately 2 h prior to IMP administration.

Subjects will take rifampicin for 9 consecutive days; from Day -9 to Day -1 of Period 4. All doses of rifampicin should be taken with approximately 240 mL water at approximately the same time each morning, prior to eating breakfast.

Part 2

Subjects will take omeprazole for 4 consecutive days; from Day -3 to Day 1 of Period 2. All doses of omeprazole should be taken with approximately 240 mL water. On Days -3 to -1 (Period 2 only) subjects should take omeprazole at approximately the same time each morning prior to eating breakfast. On Day 1, omeprazole will be administered in the fasted state, approximately 2 h prior to IMP administration. Decaffeinated fluids will not be allowed from 1 h prior until 1 h post-omeprazole administration (except on Day 1; see Section 11.1.1 Part 2 for details).

